7.3.4 Antiarrhythmic Drug (AAD) Therapy

If the subject is being maintained on beta blocking agents, calcium channel blockers or digitalis for a condition other than for AAD purposes, this medication shall be maintained throughout the duration of the subject's involvement in this investigation unless deemed unnecessary or detrimental to the subject by the treating physician.

- Procedure through 90 days (blinking period)

After the ablation procedure, subjects may be placed on AAD therapy:

- As prophylaxis for early AF recurrence
- For treatment of left atrial flutter

A new medication or a previously prescribed medication may be used.

It is recommended to withdraw AAD therapy 4-6 week post procedure to evaluate the subject's arrhythmia status.

- If symptomatic AF recurs following removal of AAD therapy during the blinking period, subjects may be offered an additional ablation procedure and/or placed on long term AAD therapy at the discretion of the investigator with a previously ineffective, but tolerated AAD dose.
- Class I, Class II, Class III and Class IV drugs may be used except amiodarone
- It is recommended that subjects be started on long term AAD therapy no later than 1-2 weeks prior to the end of the blinking period to ensure that adequate dosing is achieved.
- 91 - 365 days (after the blinking period)
 - Subjects may continue or start a previously used AAD medication up to the maximum historical dose 2 years prior to the procedure

As a component of the primary effectiveness endpoint, success with respect to AAD therapy is defined as:

- Freedom from AAD therapy from 90-365 days (after the blinking period)
- Use of previously used AAD medication from 90-365 days which does not exceed the maximum historical dose 2 years prior to the procedure

An AAD failure is defined as:

- Use of previously used AAD medication from 90-365 days (after the blanking period) which exceeds the maximum historical dose 2 years prior to the procedure
- New AAD therapy (not previously taken prior to procedure or during the blanking period) started after the blanking period

This antiarrhythmic treatment strategy is based on the NaviStar® ThermoCool® IDE study. The strategy acknowledges that it is common practice to reinstitute antiarrhythmic drug therapy to attempt to control the AF.

7.3.5 Pre-Discharge Evaluation

Subjects will be evaluated for any change in antiarrhythmic, anti-platelet or anticoagulation medication from baseline medication, Major Complications (MC) and adverse events (AE) **before hospital discharge or within 48 hours, whichever comes first**. The following evaluations will be performed at this pre-discharge visit:

- Record any changes in baseline anticoagulants, anti-platelets, or anti-arrhythmic medications,
- Major Complications,
- Adverse events,
- CBC,
- BUN/CR,
- 12-lead ECG,
- Physical examination, including pulse rate, respiration rate, and blood pressure.

7.3.6 Follow-up Evaluation

7 days (± 3 days) post procedure

A scripted phone call will be made to the subject to assess for Major Complications, concomitant medications (antiarrhythmic, anti-platelet, anticoagulation, or proton pump inhibitor) and adverse events since discharge from the hospital.

30 days (± 14 days) post procedure

Subjects will be asked to return for a follow-up visit at 30 ± 14 days. At this follow-up visit, subjects will undergo an evaluation for changes in medications (antiarrhythmic, anti-platelet or anticoagulation), Major Complications and adverse events. The following evaluations will be performed at this follow-up visit:

- Physical examination including, pulse rate, respiration rate, and blood pressure,

- NYHA classification,
- Concomitant medications (antiarrhythmic, anti-platelet, anticoagulation, or proton pump inhibitor),
- 12-lead ECG,
- Major Complications,
- Adverse events.

90 days (\pm 14 days) post procedure

Subjects will be asked to return for a follow-up visit at 90 days (\pm 14 days). At this follow-up visit, subjects will undergo an evaluation for changes in medications (antiarrhythmic, anti-platelet or anticoagulation), Major Complications and adverse events. The following evaluations will be performed at this follow-up visit:

- Physical examination,
- NYHA classification,
- Concomitant medications (antiarrhythmic, anti-platelet or anti-coagulation),
- 12-lead ECG,
- Event recorder issued to subject at this visit to be in effect through day 365 (1 year) to document symptomatic recurrence of AF. Asymptomatic trans-telephonic monitoring (TTM) is required weekly for the first 8 weeks and for any symptomatic episodes. After 8 weeks, asymptomatic transtelephonic monitoring is required once per month and with symptomatic episodes throughout the end of the study.
- Major Complications,
- Adverse events,
- Discontinuation of AAD.

180 days (\pm 30 days) post procedure

Subjects will be asked to return for a follow-up visit at 180 days (\pm 30 days). At this follow-up visit, subjects will undergo an evaluation for changes in medications (antiarrhythmic, anti-platelet or anticoagulation), Major Complications and adverse events. This visit will specifically evaluate the presence of esophageal injury or pulmonary vein stenosis.

The following evaluations will be performed at this follow-up visit:

- Physical examination,
- NYHA classification,

- Concomitant medications (antiarrhythmic, anti-platelet or anticoagulation),
- 12-lead ECG,
- 24 hour Holter monitor,
- Cardiac CT or MR*,
- Major Complications,
- Adverse events.

Note: The safety CT/MR imaging must have the same Imaging parameters as the Baseline. For example, if a CT performed at baseline, a CT must be performed at this visit with the same imaging specifications.

365 days (\pm 30 days) post procedure

Subjects will be asked to return for a follow-up visit at 365 (\pm 30 days). At this follow-up visit, subjects will undergo an evaluation for changes in medications (anti-arrhythmic, anti-platelet or anticoagulation), Major Complications and adverse events. The following evaluations will be performed at this follow-up visit:

- Physical examination,
- NYHA classification,
- Concomitant medications (antiarrhythmic, anti-platelet or anticoagulation),
- 12-lead ECG,
- 24 hour Holter monitor,
- Major Complications,
- Adverse events,
- Cardiac CT or MR: *only required in subjects showing more than 50% narrowing of a pulmonary vein at the 180 day cardiac CT or MR imaging. The imaging modality and parameters must be the same as the initial baseline imaging.*
- Study Exit.

If at any time during the follow-up period a subject shows potential signs of pulmonary vein stenosis or atrio-esophageal fistula, the standard of care should be followed inclusive of the appropriate imaging for diagnosis. All reports of imaging done outside of the protocol required follow-up are to be forwarded to the Sponsor.

Table 9: Schedule of Study Assessments

	Screening/ Baseline (testing within 30 d)	Pre- Procedure (within 24 hrs.)	Procedure	Pre- Discharge	7-Day Follow-up (± 3d)	30 Day Follow-up (± 14d)	90 Day Follow-up (±14d)	180 Day Follow-up (± 30d)	365 Day Follow-up (± 30d)
Informed Consent	X								
Demographics and Medical History	X								
Physical Exam/Vital Signs	X			X		X	X	X	X
Medication History ¹	X			X	X	X ¹	X	X	X
Cardiac CT/MR*	X ⁸							X ¹¹	
12 lead ECG	X	X	X ⁹	X		X	X	X	X
NYHA Class	X					X	X	X	X
TEE/ICE		X ⁵							
TTE	X ¹⁰		X ⁶						
Esophageal temperature monitoring			X						
24 hr. Holter Monitor								X	X
Event Recorder (3 thru 12 months)							X ⁷	X	X
CBC	X			X					
BUN/Creatinine	X			X		X ⁴			
INR ²	X	X							
Pregnancy Test (within 7 days)		X ³							
Adverse Events			X	X	X	X	X	X	X
Device Performance			X						
Proton Pump Inhibitor Administration				X	X	discontinue			

1. Antiarrhythmic Anti-platelet, Anticoagulation

2. Only if subject on anticoagulation therapy

3. Within 7 days of Procedure. Applicable to female of childbearing potential.

4. Applicable only to subject in chronic renal failure or who had an elevated creatinine during index hospitalization.

5. Within 24 hours of procedure, or at the onset of the procedure for both structural and thrombus evaluation.

6. TTE, TEE, ICE or IVUS required prior to ablation catheter insertion and 5 minutes after ablation catheter removal.

7. Each subject is to be given an event recorder at the 90 day visit. Subjects should continue to use event recorder as instructed thru the 365 day f/u visit.

8. Within 3 months of initial ablation procedure

[figure not shown]
9. Done at end of procedure prior to leaving EP lab.

10. Within 3 months prior to procedure

11. Subjects showing pulmonary vein (PV) narrowing of more than 50% at 180 day f/u visit shall have a cardiac CT or MR scan to evaluate for PV stenosis at 365 days.

*Note: If a CT or MR is performed at baseline, the same imaging specifications must be used at the follow-up visit for 180 and 365 days.

Figure 5: Study Algorithm for Subject Participation

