5.3 Primary Effectiveness Endpoint

The primary effectiveness endpoint is chronic success. Chronic success is defined to be:

- Freedom from symptomatic atrial fibrillation, atrial flutter, and atrial tachycardia episodes from days 91 - 365 after the initial ablation procedure, as documented by event recording, ECGs, and Holter monitoring.
- No use of Class I, Class II, Class III or Class IV antiarrhythmic medications during days 91 - 365 after the initial ablation procedure with the following exceptions.
 - Addition of Anti- Arrhythmic (AAD) medication which was previously ineffective for AF and does not exceed the previous historical maximum dosage (24 hour total dose).
 - Use of Atrioventricular (AV) nodal blocking agents such as beta blockers (BB) and/or calcium channel blockers (CCB) that are maintained at the current dose (does not exceed previous historical maximum dosage (24 hour total dose).
- No more than two additional ablation procedures within 90 days of the initial ablation procedure and no additional ablation procedures after day 90.
- No use of a non-study device for ablation of any atrial fibrillation target. Commercially available non-study devices may be used for atrial flutter and atrial tachycardia ablation targets.
- No ablation of an atrial fibrillation target made by removing the ablation catheter from the Artisan catheter and manually manipulating the ablation catheter.
- Pulmonary vein isolation of at least 3 out of 4 veins confirmed by pulmonary vein entrance block during the last procedure within the blanking period.
- No surgical ablation for atrial fibrillation, atrial flutter, or atrial tachycardia within 90 days of the initial ablation.
- No direct current (DC) cardioversion for atrial fibrillation, atrial flutter, or atrial tachycardia within days 91 - 365 after the initial ablation procedure.
- No catheter or surgical ablation for atrial fibrillation, atrial flutter, or atrial tachycardia within days 91 - 365 after the initial ablation procedure.

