7.3.2 Pre-Procedure Evaluation – Within 24 hours of procedure

Within 24 hours prior to the initial ablation the following will be done:

- Blood will be drawn to measure for INR value*,
- 12-lead electrocardiogram (ECG) performed to check for cardiac rhythm and indication of myocardial ischemia,
- TEE/ICE should be performed to assess for possible atrial thrombus 24 hours prior to procedure or the day of the procedure. Also to establish that thrombus, cardiac structure, function, LA size and EF meet protocol criteria.

**If subject's INR is minimally >3.0 within 24 hours pre-procedure, another INR may be done on day of procedure, if INR results < 3.0, subject may be enrolled.*

Table 8: Definition of Study Time Points

Interval	Time Point and Window (if applicable)
Screening/Baseline	Within 30 days except for pregnancy test (within 7 days), from initial ablation
Pre-procedure	Within 24 hours prior to the initial ablation.
Enrollment	Subject is considered to be enrolled once they sign the Informed Consent Form.
Discharge	0 – 48 hours or prior to discharge; whichever comes first.
7-Day Follow-up	7 days \pm 3 days.
30-Day Follow-up	30 days \pm 14 days post initial ablation procedure.
90-Day Follow-up	90 days \pm 14 days post initial ablation procedure.
180- Day Follow-up	180 days (6 months) \pm 30 days post initial ablation procedure.
365- Day Follow-up	365 days \pm 30 days post initial ablation procedure.

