7.6.2 Holter Monitoring and Event Recording

A core laboratory will be used to evaluate the events obtained from the 24-hour Holter monitors and ECG data at the 6 and 12 month follow-up visits for recurrence of an atrial arrhythmia (atrial fibrillation, atrial flutter or atrial tachycardia) episode. Initial

evaluations will be done by a technical person trained in the evaluation for these tests and the initial evaluations will be affirmed by a physician.

In addition to the clinical sites following the study subjects, the core lab also will track the subjects to ensure that each subject remains active in the use of their event monitor.

Subjects will be provided a TTM monitor at the 90-day visit. The core lab will create and provide copies of the required TTM schedules for subjects to transmit their weekly and monthly transmissions in accordance with the protocol requirements. Subjects are required to submit asymptomatic readings weekly for 8 weeks following the blanking period, then once a month on a monthly basis for the remainder of the study. Study subjects also will be instructed to use the event monitor at any time following their 90 day through day 365 follow up visit for any recurrence of their symptoms. The core lab will accept subject transmission 24 hours a day and 7 days per week. If a study subject misses their scheduled transmission, the core lab will contact the site until the subject is reached and a transmission has been received.

Study subjects will be considered compliant with the use of the TTM device if they transmit within ± 3 days of their scheduled transmission date and achieve at least 80% of their scheduled transmissions. If the TTM compliance rate is less than 80%, it will be considered as a major protocol deviation.

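### Recorder issue and end dates do not guarantee event-recorder cover of the whole day 91–365 endpoint window: up to 13 days can be missing at the start, and up to 30 more at the end if the final visit governs

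*Protocol*

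**What the plan says.** - **Endpoint window.** Protocol 5.3 requires "Freedom from symptomatic atrial fibrillation, atrial flutter, and atrial tachycardia episodes from days 91 - 365 after the initial ablation procedure", and counts recurrence "as documented by event recording, ECGs, and Holter monitoring".
- **Start of recording.** Section 7.3.6 places issue of the recorder at the 90-day visit. Table 8 gives that visit a window of ±14 days, so days 76 to 104. Nothing in the protocol requires issue by day 90.
- **End of recording, first statement.** Section 7.3.6 says: "Event recorder issued to subject at this visit to be in effect through day 365 (1 year) to document symptomatic recurrence of AF". The synopsis also gives day 365.
- **End of recording, second statement.** Table 9 footnote 7 says: "Subjects should continue to use event recorder as instructed thru the 365 day f/u visit". Section 7.6.2 likewise refers to the visit: "Study subjects also will be instructed to use the event monitor at any time following their 90 day through day 365 follow up visit".
- **Final visit.** Table 8 gives the 365-day visit a window of ±30 days, so days 335 to 395. Section 7.3.6 lists study exit among the items of that visit.
- **Missing outcomes.** The missing-data paragraph at the end of section 6.8 has missing final outcomes multiply imputed with a piece-wise exponential time-to-event model, and refers to Appendix M for details. Appendix M is not in the text at hand.

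**The concern.** The endpoint is fixed in calendar days from the ablation, while the main tool for detecting symptomatic recurrence starts, and on one reading stops, at visits with wide windows. A subject can therefore comply fully with the schedule and still have endpoint days on which no recorder was available.

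For the recurrence component, a missed episode can only turn a failure into an apparent success. The trial has one arm and compares its rate with a fixed 54% goal, so there is no concurrent control in which the same loss would occur. Any error of this kind therefore raises the chance of meeting the goal.

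**Working it through.** The protocol states no figure for recorder coverage, so there is none to reproduce. The check has two parts.

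**1. Days without a recorder**

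- Endpoint window: 365 − 91 + 1 = 275 days.
- Latest issue, 90 + 14 = day 104: days 91–103 are uncovered, 13 days (13/275 = 4.7%).
- Earliest final visit, 365 − 30 = day 335: days 336–365 are uncovered if recording stops there, 30 days (30/275 = 10.9%).
- Both together, the worst case for one subject: 43 days (43/275 = 15.6%).
- Visits on target (day 90 and day 365): 0 days.
- Recording through day 365 regardless of the visit, with issue still possible on day 104: at most 13 days.

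**2. Upper bound on the bias**

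Assumptions, none of them stated in the protocol: constant hazard over the 275 days; visits spread evenly over their windows; recording stops at the final visit; every failure is a recurrence; every subject whose first recurrence falls in a gap is never detected; Beta(1,1) prior; fixed N = 250 with no interim looks.

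- Average gap at the start: (13²/2)/28 = 3.0 days.
- Average gap at the end: (30²/2)/60 = 7.5 days.
- Total: 10.5 days.
- Apparent success when the true rate is 54%: 0.54^((275 − g)/275), where g is the gap in days.
- Passing rule from section 6.2 (at least 95% of the posterior above 54%): with the assumed prior this needs 148 successes out of 250.
- Probability of passing: P(X ≥ 148), with X binomial(250, apparent rate).

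| Gap applied | g (days) | Apparent success | P(pass) |
|---|---|---|---|
| None | 0 | 54.0% | 5.6% |
| Average, start only (recording runs to day 365) | 3.0 | 54.4% | 7.0% |
| Average, start and end | 10.5 | 55.3% | 11.9% |

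If only a quarter of the events in the 10.5-day gap were truly lost (an illustration), apparent success would be 0.54 + 0.25 × (0.5529 − 0.54) = 54.3%, and the probability of passing 6.8%.

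**The case against.** A reader might infer that 43 of the 275 endpoint days go unmonitored and that recurrences in them are lost. The documents do not support that, for four reasons.

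- **The recorder is not the only source.** ECG and Holter also count under 5.3. The definition of symptomatic AF in section 15 involves seeking medical attention, with the episode documented by any of the three. A symptomatic subject on days 91–103 can be captured by a clinical ECG; a late 90-day visit includes a 12-lead ECG, and an early final visit includes an ECG and a 24-hour Holter. A subject is misclassified only if every documentable recurrence falls in a gap. This stands. However, scheduled ECGs and Holters fall only at visits, and no scheduled study contact remains after exit.
- **The 30 days at the end depend on which passage governs.** Section 7.3.6 and the synopsis say day 365, and the Table 9 row covers months 3 to 12. The end gap is the possible result of a conflict in wording. The 13 days at the start do not depend on it.
- **Early exits may already be imputed.** No passage says that an event-free exit on day 335 counts as a success, and Appendix M may settle the matter. This stands too. Imputation by exit date would not, however, repair a start gap, when the subject is still in follow-up.
- **The size is easily overstated.** Putting every subject at exit on day 335 gives 57.8% apparent success and a 35% chance of passing; adding issue on day 104 for all gives 59.5% and 56%. Such a trial is not plausible. Several failure criteria in 5.3 (incomplete vein isolation, manual or non-study ablation of an AF target, drug use, cardioversion, later ablation) do not need a recorder at all.

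Finally, section 6.6 calls the endpoints of the study behind the 54% goal equivalent. If its visit windows and recorder timing were similar, part of the bias would be common to both. Those details are not given, so this can be neither relied on nor dismissed.

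**Conclusion.** The point holds as a gap in scheduling and a contradiction in wording. Up to 13 of 275 endpoint days can pass without a recorder on any reading. Up to 30 more can do so if recording ends at the 365-day visit. Recurrences confined to those days and not otherwise documented may be missed, and the resulting bias can only run toward success.

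Under the assumptions listed, the bias is at most about 1.3 percentage points on average (54% appearing as 55.3%), with the chance of passing at the goal rising from 5.6% to about 12%. If recording does run to day 365, the corresponding bound is 54.4% and 7.0%. The real effect is smaller in either case, because recurrences tend to repeat, other sources can document them, and not all failures are recurrences. The correction is worth making because it is cheap and the direction of the error is known.

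**What to change.** - Reconcile 7.3.6, 7.6.2 and Table 9 footnote 7 so that they give one start and one end for recording.
- Have the recorder in the subject's hands by day 90, for example by sending it ahead when the visit will be late.
- Continue recording to day 365 whatever the date of the final visit, and do not allow study exit before day 365.
- State that a subject who leaves event-free before day 365 has incomplete follow-up and is handled by the planned imputation, not counted as a success. If Appendix M already says so, a cross-reference is enough.

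With these changes the gap is 0 of 275 days. The cost is protocol wording and scheduling, a narrower final-visit window, and a few more visit deviations.

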15.0 Study Definitions

AF Episode: An episode of AF 30 seconds or longer in duration on Holter or Trans-telephonic Monitoring (TTM), or 10 seconds in duration on 12-lead ECG.

Atrial Tachyarrhythmia Episode: An episode of atrial tachycardia, tachyarrhythmia (atrial fibrillation, atrial flutter or atrial) 30 seconds or longer in duration on Holter or Trans-telephonic Monitoring (TTM), or 10 seconds in duration on 12-lead ECG.

Blanking period: 90 day period between the index ablation procedure and the continuation of the 12 month follow-up period. If a subject is symptomatic during the 90 day blanking period, he/she may be placed on a previously ineffective Anti arrhythmic Drug (AAD). If a subject remains symptomatic, the AAD dose may be increased, a new AAD added, or the subject may be treated again using the Hansen System up to two more times before day 90. At the 90 day visit, subject will need to discontinue any class I, class II, class III and class IV AADs or maintain AAD's that were ineffective at baseline, at a dosage level less than or equal to the maximum baseline dosage. Calcium channel and beta blocker medications may continue for uses other than an antiarrhythmic drug.

Bleeding: A Major Complication of AF ablation if it requires and/or is treated with transfusion or results in a 20% or greater fall in HCT.

Discontinued Subjects: Subjects in whom the ablation catheter was inserted but did not undergo ablation or attempted ablation (no RF energy applied). Subjects are considered ‘discontinued’ if ablation was not possible due to non-study equipment failure or if their arrhythmia was determined to be a non-study arrhythmia (e.g. atrial flutter). These subjects will be followed for 7 days for safety endpoint evaluation.

Enrollment: Subject is considered to be enrolled once they have signed the informed consent form.

Paroxysmal AF: An atrial fibrillation where a subject has two or more spontaneously terminating episodes of atrial fibrillation that last longer than 30 seconds and shorter than seven days.

Screening Failure: Subject is excluded from enrollment from the study if they do not meet 1 or more of the pre-operative inclusion/exclusion criteria.

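### The antiarrhythmic-drug component of the primary effectiveness endpoint is defined one way in Section 5.3 and more leniently in Section 7.3.4

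*Protocol*

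**What the plan says.** **Section 5.3 and the synopsis** bar Class I-IV drugs on days 91-365 with two exceptions. One is an AAD that was earlier ineffective for AF, at or below the historical maximum 24-hour dose. The other is an AV nodal blocker kept at its current dose.

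**Section 15.0** (Blanking period) agrees with 5.3 for the 90-day visit: "At the 90 day visit, subject will need to discontinue any class I, class II, class III and class IV AADs or maintain". The alternative it allows is "or maintain AAD's that were ineffective at baseline, at a dosage level less than or equal to the maximum baseline dosage".

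**Section 7.3.4** states its own rule and expressly labels it a component of the primary effectiveness endpoint.
- Permission for days 91-365: "Subjects may continue or start a previously used AAD medication up to the maximum historical dose 2 years prior to the procedure".
- Success includes: "Use of previously used AAD medication from 90-365 days which does not exceed the maximum historical dose 2 years prior to the procedure".
- Failure is a previously used drug above the cap, or: "New AAD therapy (not previously taken prior to procedure or during the blanking period) started after the blanking period".

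Only for long-term AAD therapy begun during the blanking period does 7.3.4 add that treatment be "with a previously ineffective, but tolerated AAD dose".

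**Section 7.3.6** ends its list for the 90-day visit with "Discontinuation of AAD" and gives no alternative.

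**Section 6.2** tests chronic success against 54% with a 95% posterior rule and refers to 5.3 for the additional criteria.

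**The concern.** A drug that was used before is not necessarily a drug that was ineffective before. Inclusion criterion 2 accepts intolerable side effects as an alternative to recurrent symptomatic AF, so the trial can enrol subjects whose earlier AAD was stopped without ever being shown ineffective. For such subjects the two rules can give different primary endpoint results, and 7.3.4 is the more lenient.

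This is a single-arm study judged against a fixed goal, so there is no control arm in which a lenient rule would apply equally. Any slack in classification moves the observed rate directly against 54%. Section 1.2 says that Revision J changed the AAD evaluation to make it equivalent to the analysis of the comparator IDE study, so an ambiguous rule also undercuts the sponsor's own purpose.

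**Working it through.** **Step 1. Classify four cases under each rule (days 91-365, all other criteria met).**

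| Case | Section 5.3 / synopsis | Section 7.3.4 |
|---|---|---|
| Class I or III drug, earlier ineffective for AF, dose at or below cap | Excepted: not a failure | Success |
| Class I or III drug, stopped earlier only for intolerance, restarted after day 90, dose at or below cap | No exception: failure | Success (previously used, within cap) |
| Class I or III drug first taken in the blanking period and continued after day 90 | No exception: failure | Not a failure: excluded from the new-drug definition |
| Class I or III drug never taken before day 91 | Failure | Failure |

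The rules agree on rows 1 and 4 and disagree on rows 2 and 3. Row 3 is not plainly a success under 7.3.4 either, because its dose cap refers to the two years before the procedure and such a drug has no dose in that period. It simply escapes the failure definition. Section 15.0 sides with 5.3 on both rows.

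Row 3 is a realistic path: 7.3.4 allows a new medication during the blanking period.

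**Step 2. Weight of one reclassified subject.** 1/125 = 0.8 percentage points; 1/250 = 0.4 points.

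**Step 3. Successes needed.** Inputs: goal 54% and posterior probability of at least 95% (6.2). The prior is in Appendix M, which is not shown, so a flat Beta(1,1) prior, complete outcomes and a fixed n are assumed. Find the smallest x with P(p > 0.54 | Beta(1+x, 1+n−x)) ≥ 0.95.

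| n | x | Posterior at x | Posterior at x − 1 | x/n |
|---|---|---|---|---|
| 125 | 77 | 0.955 | 0.935 | 61.6% |
| 250 | 148 | 0.950 | 0.935 | 59.2% |

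A Jeffreys prior gives the same 77 and 148.

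**Step 4. Reclassifications that would lose the claim.** Suppose the 7.3.4 rule produced the expected count at the comparator's 64% (6.6) or at the planning rate of 72% (6.5).

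| Rate | n | Expected successes | Moves needed to fall below the rule | Share of n |
|---|---|---|---|---|
| 64% | 125 | 80 | 80 − 76 = 4 | 3.2% |
| 64% | 250 | 160 | 160 − 147 = 13 | 5.2% |
| 72% | 125 | 90 | 90 − 76 = 14 | 11.2% |
| 72% | 250 | 180 | 180 − 147 = 33 | 13.2% |

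**Step 5. Effect on effectiveness power.** The same thresholds, with exact binomial tails. The documents give no share of affected subjects, so a range is assumed for the drop from 72% under the stricter reading.

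| Assumed drop | n = 125 | n = 250 |
|---|---|---|
| 2 points (70%) | 98.2% | 99.99% |
| 5 points (67%) | 91.5% | 99.6% |
| 10 points (62%) | 57.6% | 83.6% |

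These are fixed-n approximations for scale. They do not reproduce the adaptive design's stated 98%, which covers both endpoints.

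**The case against.** **Section 5.3 already controls.** It carries the endpoint's title, matches the synopsis, and is where 6.2 sends the reader. This is a fair textual reason to prefer 5.3, and it makes the classification less open than two equal definitions would. It does not settle the matter, because 7.3.4 also calls its rule part of the primary endpoint and no precedence is stated.

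**The affected group is narrow.** Row 2 needs a subject who restarts the same drug that was stopped for side effects, within the cap, and meets every other criterion. Beta blockers and calcium channel blockers at the current dose are excepted separately in 5.3. This stands, though row 3 needs no such unusual path.

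**The figure of 4 in 125 is a worst case.** It pairs a 64% result with the smallest final sample. Enrolment stops for expected success only when both endpoints have at least a 95% predicted chance of success, so a trial running at 64% would often continue past 125. This stands.

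**The 90-day item in 7.3.6.** A reader might infer that every AAD must be stopped at day 90, in conflict with 15.0 and 7.3.4. The text does not support a flat prohibition. The item sits in a list of evaluations, can be read as something to record, and is not repeated in Table 9 or the synopsis follow-up list. Because that list also has a medication item and includes an action (issuing the event recorder), a site could take it as an instruction. That would tend to lower the success rate and would misclassify nobody on the AAD component. It is an incomplete restatement and no more.

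**Conclusion.** The conflict is real: 5.3 and 7.3.4 both define the AAD component, and they disagree on drugs stopped only for intolerance and on drugs first started in the blanking period. The text alone establishes this, with no assumption about the prior.

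Its numerical effect cannot be derived from the protocol. Under the flat-prior, fixed-n, complete-data assumptions it is probably small at the planning rate and could change the conclusion only if the observed rate lies near the decision threshold of roughly 59% to 62%.

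A reader might infer that the effectiveness claim is inflated, or that 7.3.4 should simply be tightened. The protocol supports neither. It does not show how many subjects are affected, and it does not show which term matches the comparator study's analysis, from which the 54% goal was derived. The severity is minor, and confidence that the two definitions conflict is high.

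**What to change.** 1. State which definition controls. Section 5.3 is the default, since 6.2 refers to it. First confirm that it matches how the comparator IDE study behind the 54% goal classified AAD use; if it does not, correct 5.3, the synopsis and 15.0 instead.
2. Rewrite the days 91-365 permission in 7.3.4, and its success and failure definitions, to match the controlling text.
3. Add a sentence on how two cases are classified: a drug stopped earlier only for intolerance, and a drug first started in the blanking period and continued after day 90.
4. Editorial: change the 7.3.6 item to *Discontinuation of AAD, or continuation of a permitted AAD at or below the maximum historical dose, per 7.3.4 and 15.0*. Leave beta blockers, calcium channel blockers and digitalis taken for other conditions to 7.3.4, which keeps them "unless deemed unnecessary or detrimental to the subject by the treating physician".

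The cost is a few aligned sentences, a check against the comparator's analysis and a clarification to sites. No visits, tests or subjects are added.
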